**FORM: Application for Human Research**

NUMBER	FORM DATE	PAGE
F200		13 of 18

Therapy Systems, Mesa, AZ) as a non-significant risk device. (Please see the attached NSR statement.) Adverse events will be recorded at each visit (see appendix 4 of the protocol).

Additionally, x-rays will be obtained as part of the standard care. A small risk exists of developing cancer later in life as a result of exposure to radiation.

Finally, risk of exposure of protected health information (PHI) exists. However, we have minimized this risk by implementing three levels of precaution. Access to protected health information will be restricted to the minimum number of individuals required to complete the tasks. The files containing the PHI will be kept electronically and geographically separate from the data files with entries identified only by a randomly generated number to be used as the PHI key. Both files will be encrypted and password protected and then stored on password protected, secured computers.

9) Potential benefits to subjects and/or society

Subjects receiving intensive therapeutic ultrasound treatment may experience faster healing time, decreased pain and return to full function earlier as a result of the treatment. Patients not placed into the ITU group will receive no additional individual benefit by participating in the study. The results of this study may lead to further research or widespread clinical application of ITU in turn increasing knowledge in this area or improving the care available to individuals affected by plantar fasciitis. However, in general the subjects will obtain no significant benefit by participating in the study.

10) Provisions to protect the privacy of subjects and the confidentiality of data

The consenting process will be initiated in the clinic with the physicians in the privacy of an exam room. The names and contact information for potential subjects will be kept in a password encrypted excel file on a password protected, secured computer. Only the minimum number of research personnel required to complete the consenting process will have access to PHI. Once enrolled in the study a unique patient identifier will be used in subsequent date files generated in the study. . A list linking subjects to identifiable information will be stored on a password protected, secured computer. This list will only be accessible to the study coordinator during the study and to the PI (L [name] PhD) following data analysis. Should the arrival of subjects in the lab overlap, we will have a separate room available apart from the lab so that the consenting and subsequent exam and treatment can be conducted in privacy. Should a participant decide to leave the study, the patient's PHI records will be destroyed, but the data will be retained. Upon closure of the IRB project, all patient identifiers will be destroyed.

11) Access to Private Information**a. Authorization for access to Protected Health Information (PHI)**

We are requesting a temporary waiver of authorization so that we may obtain contact information from the medical records for those subjects identified in clinic as interested in the study. We will obtain authorization for PHI during the consenting process. This request is based upon the following justification-

**FORM: Application for Human Research**

NUMBER	FORM DATE	PAGE
F200		14 of 18

- 1) The use or disclosure of protected health information involves no more than minimal risk to the privacy of individuals, based on , at least, the presence of the following elements;
 - a) An adequate plan to protect the name and phone number from improper use and disclosure has been implemented through the utilization of password protected files. Additionally, the PHI will be obtained and accessed only by the minimal number of investigators required to conduct the study. Furthermore, the computer containing the PHI will be password protected and secured.
 - b) An adequate plan to destroy the identifiers at the earliest opportunity consistent with conduct of the research, unless there is a health or research justification for retaining the identifiers or such retention is otherwise required by law, has been implemented in that the contact information will be destroyed if the subject declines participation. An authorization will be obtained prior to the additional collection of PHI.
 - c) Adequate written assurances that the protected health information will not be reused or disclosed to any other person or entity, except as required by law, for authorized oversight of the research study, or for other research for which the use or disclosure of protected health information would be permitted by HIPAA, are hereby provided in that the PHI will only be utilized to conduct the study as described within the attached protocol.
- 2) The research could not practicably be conducted without the waiver or alteration of the HIPAA authorization requirement because access to contact information is required to begin the process of informed consent. If the subject indicates that they are not interested in participating, their contact information will be removed from the encrypted data file. No other information will be obtained from the records until authorization is provided by the subject.
- 3) The research could not practicably be conducted without access to and use of the protected health information because obtaining authorization at the clinic for participation in the study may not be consistently feasible.

12) Cost to subjects

The proposed research has no associated costs to the subjects.

13) Subject compensation

The subjects will not be compensated.

14) Medical care and compensation for injury

If an injury occurs, medical care is available. No funds are available to cover compensation for any injury incurred as a result of participation in this investigation.

15) Withdrawal of subjects

Subjects may withdraw from the study at any time either in person, in writing, or by telephone. Subjects withdraw by contacting either [name] or the project lead. Abrupt withdrawal

**FORM: Application for Human Research**

NUMBER	FORM DATE	PAGE
F200		15 of 18

presents no risk. Should subjects fail to comply with instructions given to them, they may be withdrawn from the study.

16) Sharing of results with subjects

The results of the study will not be shared with subjects.

17) Information management

N/A

18) Drugs, Devices, and Gases

Equipment for intense therapeutic ultrasound will be provided by [name] and [name] from Guided Therapy Systems and operated by trained sonographers.

- a) Name of drug/device: GEN II
- b) FDA approval status of the drug/device: We are seeking classification as a Non-Significant Risk (NSR) Device with the following reasons-
 - (a) GEN II will not be utilized nor is intended to be utilized as an implant. Additionally, the device does not present a potential for serious risk to the health, safety, or welfare of a subject.
 - (b) GEN II is not purported or represented to be for a use in supporting or sustaining human life and does not present a potential for serious risk to the health, safety, or welfare of a subject.
 - (c) The GEN II device is not of substantial importance in diagnosing, curing, mitigating, or treating disease, or otherwise preventing impairment of human health and does not present a potential for serious risk to the health, safety, or welfare of a subject.
 - (d) The GEN II does not otherwise present a potential for serious risk to the health, safety, or welfare of a subject.
- c) The GEN II will be controlled by the PI and/or representatives of the sponsor, Guided Therapy Systems:
 - i) The device will be stored in the PI's laboratory located in the Department of Orthopaedic Surgery, Biological Research Buildings, Building B Room 101 or in possession of GTS representatives.
 - ii) The site is sufficiently secure to protect the equipment.
 - iii) The storage condition for the equipment is not of concern beyond normal sheltered conditions.
 - iv) The GEN II device does not require stringent control and tracking of utilization.

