**FORM: Application for Human Research**

NUMBER	FORM DATE	PAGE
F200		9 of 18

to heal will be compared for traditional treatment methods + placebo to that required by traditional treatment + ITU. Every subject will receive anti-inflammatory medication, a viscoelastic heel cup, and physical therapy. Patients receiving just these treatments will be compared to those also receiving ITU treatments. Who can participate? The following criteria are required for participation: A physician associated with the study has diagnosed you with plantar fasciitis. To be eligible you need to have chronic heel pain that is diagnosed as plantar fasciitis by a physician associated with the study. The/your symptoms exist in only one foot. You must not have diabetes or be pregnant. You must be 18 years or older. What will participation require? You will need to be assigned to either a control group (standard medical care) or to an experimental group (standard medical care + ITU). You will need to not use any other treatments. You will need to commit to the assigned treatment for 3 months. You will need to answer an additional online or telephone questionnaire at 6 months. Why should I participate? Although you will not receive payment, what is learned may benefit others! To participate, please call [contact information]. If interested, please call [contact information] or send an email to [contact information] and provide preferred contact information."

In addition to anatomical labeling of the *achilles tendon, calcaneus, and plantar fascia*, we would like to use the captions, "*Inflammation of the plantar fascia can cause heel pain*" and "*stretching the plantar fascia*."

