**FORM: Application for Human Research**

NUMBER	FORM DATE	PAGE
F200		10 of 18

Table 1. Calendar of Activities

Timeline	Standard of Care	Research Activity
-1	focused history, x-rays, NSAIDs, heel cups	Informed consent and assessment of inclusion/exclusion criteria; enrollment in the study (randomization to treatment group)
0	NSAIDs, heel cups, focused exam	questionnaires; ultrasound (diagnostic & treatment)
2 weeks	NSAIDs, heel cups, focused exam	questionnaires; ultrasound (diagnostic & treatment)
4 weeks	heel cups, focused exam	questionnaires ultrasound (diagnostic)
6 weeks	heel cups, focused exam	questionnaires ultrasound (diagnostic)
12 weeks	heel cups, focused exam	questionnaires ultrasound (diagnostic)
24 weeks		questionnaires

Structured physical examination. The focused exam will consist of assessment of hindfoot and midfoot alignment, inspection for swelling, palpation of the calcaneus and entire plantar fascia, range of motion of the ankle with the knee flexed and with the knee extended, and calcaneal squeeze test. Pertinent positive findings on exam include: valgus hindfoot, midfoot planus, tenderness to palpation at the insertion of the plantar fascia onto the calcaneus, ankle dorsiflexion less than 10 degrees with the knee extended or greater than 10 degree augmentation in ankle dorsiflexion with the knee flexed. Pertinent negative findings include: lack of swelling at the ankle and midfoot, no tenderness at the Achilles insertion, the retrocalcaneal bursae, along the arch, posterior to the medial malleolus, or at Baxters point, and positive calcaneal squeeze test.

Physical Therapy. Supervised physical therapy will occur two times per week and include gastrocnemius stretching, plantar fascia specific stretching, modalities (ice and heat), and plantar fascia deep tissue massage (see instructions to PT appendix 2 of the protocol). Use of advanced modalities such as iontophoresis, phonophoresis, or TENS will not be permitted. The home exercise program will consist of PF specific stretch and gastrocnemius stretch to be done for ten minutes two times per day (see home exercise program handout, Appendix 2 of the protocol). Subjects will be required to record the frequency of each exercise in a logbook (see Appendix 3 of the protocol).

The research components are described below-

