## Statistical Approach

- Pain Reduction:

Pain level at the plantar fascia was self-reported by subjects at pre-treatment (used as baseline measurement) and again at each follow-up - 4, 8, 12, and 26 weeks - after initial treatment. The pain scale subjects used to identify their level of pain was a 10-point pain scale range, where 0 = no pain, 1 = slight pain through 10 which equates to the patient's worst imaginable pain. The goal for all subjects in the treatment group was to reduce pain by at least 25%. Pain scores reported at follow-up timepoints were compared to baseline score for each subject to determine if the goal was met by dividing the difference in the follow-up and baseline pain score by the baseline pain score. The percentage of subjects that met the pain reduction goal was calculated at each timepoint for both control/sham-treated and treatment groups by dividing the number of subjects that achieved the pain reduction goal at each timepoint by the total number of patients that gave a pain score for that time point.

- Plantar Fascia Hypoechoic Lesion Size:

A large proportion of patients suffering from chronic plantar fasciitis present with hypoechoic lesions in or around the proximal plantar fascia, as viewed by diagnostic ultrasound imaging[7].

Hypoechoic lesions were imaged and volumes were calculated at the baseline visit and each follow-up visit by measuring the inferior-to-superior and posterior-to-anterior radii in the long axis and the medial-to-lateral radius of the transverse axis and applying the following formula for the volume of an ellipse:

$$\text{Volume} = (4/3)\pi \cdot r_1 \cdot r_2 \cdot r_3$$

With  $r_1$ ,  $r_2$ , and  $r_3$  representing the three radii detailed above. Changes to lesion volumes were recorded at each follow-up timepoint and compared to baseline by dividing the volume of the lesion at that timepoint with the volume of the same lesion at pre-treatment baseline.

- Foot Function Index Score Reduction:

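### Non-compliant subjects may be withdrawn with no criteria or further follow-up, and the SAP's observed-score denominator then distorts the pain response percentages if those withdrawn are mostly poor responders

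*Protocol*

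**What the plan says.** Protocol Section 3, item 15) Withdrawal of subjects: "Should subjects fail to comply with instructions given to them, they may be withdrawn from the study". The sentence is discretionary. It does not say which failures count, who decides, whether that person is blinded, or what data are collected afterwards.

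The instructions appear elsewhere. The recruitment wording in item 6) states "You will need to not use any other treatments" and "You will need to commit to the assigned treatment for 3 months". Item 7), Physical Therapy, adds "Use of advanced modalities such as iontophoresis, phonophoresis, or TENS will not be permitted" and requires a log of home exercises.

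Item 7), Randomization and Blinding, keeps the subject and most of the team blinded. The research coordinator and the ultrasound treatment team know the assignment.

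The SAP, Statistical Approach, Pain Reduction, defines the goal as at least a 25% fall in pain from baseline. It reports the percentage meeting that goal in both arms at 4, 8, 12 and 26 weeks. The denominator is the "total number of patients that gave a pain score for that time point". Neither document defines an all-randomised analysis set, a rule for missing scores, or a rule for scores given after use of another treatment.

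**The concern.** In a painful condition, the subject who tries something else is plausibly the one who is not improving. If that counts as non-compliance and leads to withdrawal, leaving the study is linked to outcome. Under the SAP's denominator that subject then counts neither as a success nor as a failure at later visits, so the arm's percentage rises although nobody has improved.

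The by-arm pain percentages are at stake. With a target of 50 subjects randomised 1:1, a handful of removals moves them by several points. The Foot Function Index averages in the SAP are taken by timepoint, also with no rule for missing scores, and are exposed in the same way.

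**Working it through.** **Inputs from the documents.** Target enrolment is 50 (Protocol item 5) and allocation is 1:1 (item 7), so 25 per arm if the split is exact. The responder denominator is those with a score at the visit (SAP, Pain Reduction).

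**Assumptions.** The documents give no response or withdrawal rates. I assume 15/25 = 60% responders on sham and 18/25 = 72% on ITU, which leaves 10 and 7 failures. The true difference is +12 points. The plan states no figure of its own on this point to reproduce.

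**1. Equal withdrawal per failure in both arms.** Let p be the true response rate and w the share of failures withdrawn. The apparent rate is p / (p + (1 − p)(1 − w)).

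| w | Sham | ITU | Difference |
|---|---|---|---|
| 0 | 60.0% | 72.0% | +12.0 |
| 0.3 | 0.60/0.88 = 68.2% | 0.72/0.916 = 78.6% | +10.4 |
| 0.5 | 0.60/0.80 = 75.0% | 0.72/0.86 = 83.7% | +8.7 |
| 0.7 | 0.60/0.72 = 83.3% | 0.72/0.804 = 89.6% | +6.2 |

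Both percentages are inflated and the difference shrinks. For a common w below 1 the apparent rate always rises with p, so the arms cannot change order. The shrinkage belongs to response rates in this range. At 30% v 40% with w = 0.5, the apparent rates are 0.30/0.65 = 46.2% and 0.40/0.70 = 57.1%, a difference of 10.9 against a true 10.

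**2. Unequal withdrawal per failure.** The apparent rate is responders / (25 − failures withdrawn).

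| Failures withdrawn, sham v ITU | Share of failures | Sham | ITU | Difference |
|---|---|---|---|---|
| 3 v 0 | 30% v 0% | 15/22 = 68.2% | 18/25 = 72.0% | +3.8 |
| 5 v 1 | 50% v 14% | 15/20 = 75.0% | 18/24 = 75.0% | 0 |
| 7 v 1 | 70% v 14% | 15/18 = 83.3% | 18/24 = 75.0% | −8.3 |
| 0 v 3 | 0% v 43% | 15/25 = 60.0% | 18/22 = 81.8% | +21.8 |

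Losing the difference altogether, or reversing it, takes a wide gap between arms in the share of failures withdrawn. The last row shows that the same mechanism can also exaggerate a benefit.

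**3. Opposite direction within an arm.** Suppose an arm would have 10 responders of 25 (40%), 5 of them because of the outside treatment, and those 5 are withdrawn. The SAP percentage is 5/20 = 25%, which is too low. Counting the missing as not met gives 5/25 = 20%, lower still. An all-randomised denominator is therefore not free of bias either.

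**4. Timing.** A withdrawn subject leaves only the denominators of visits after withdrawal.

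**The case against.** A reader might infer that the plan will hide or reverse a true ITU benefit. The documents do not support that. Subjects are blinded, so seeking other treatment because of poor response does not by itself produce different withdrawal rates per failure in the two arms. The coordinator knows the assignment, but no passage gives the coordinator the withdrawal decision. Selective withdrawal by arm is left open by the text, not described in it.

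A reader might also infer that the planned test of Aim 1 is invalidated. The 25% responder percentage appears only in the SAP. The t-tests there compare baseline with follow-up, and no between-arm test of these percentages is planned. The protocol's statistical analysis of patient-reported outcomes uses FFI-P, PFCAT and FAAM scores.

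A third tempting reading is that non-compliers become untraceable, because item 10) says "Should a participant decide to leave the study, the patient's PHI records will be destroyed, but the data will be retained". That sentence concerns participants who choose to leave, not those whom the team withdraws.

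Two further objections stand as limits. The ban on other treatments is recruitment wording, while item 15) speaks only of instructions. The separate ITU protocol, consent form and patient instructions are listed as attachments and are not in the text reviewed, so the absence of follow-up after withdrawal is silence rather than a stated rule.

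None of this removes the core point. A discretionary post-randomisation withdrawal without criteria, joined to an observed-score denominator and no missing-data rule, can bias percentages that the SAP does report for both arms.

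**Conclusion.** The concern holds as a conditional bias and an inexpensive improvement to the plan. If poor responders are withdrawn more often, the reported response percentages are too high and the difference between arms is distorted. On the assumed 60% v 72%, with half the failures lost in each arm, the difference falls from +12 to about +9 points. Results of zero or below need strongly unequal withdrawal, such as 50% v 14% or 70% v 14% of failures, for which the documents give no evidence. The direction is not fixed, because an outside treatment that works makes the observed percentage too low. The mechanism can be read directly from the two documents. Its size cannot, because they give neither withdrawal nor response rates.

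**What to change.** **Protocol item 15).** State that non-compliance, including use of another treatment, is recorded with its date. State also that the subject stays in the assigned group and completes all remaining questionnaires through the final visit unless consent is withdrawn. This concerns data collection only. The final visit must first be reconciled: Table 1 has week 24 and the SAP has week 26.

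**SAP.** Analyse all randomised subjects in their assigned group using every score collected, including scores after non-compliance. Report withdrawals and their reasons by arm. Beside the observed-score responder percentage, give one with all randomised subjects as the denominator and missing scores counted as not met. Keep that as a sensitivity analysis, because it penalises whichever arm has more missing scores for unrelated reasons.

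**Cost.** A few sentences in the two documents, some additional follow-up contacts, and possibly lower response percentages. The protocol allows the survey to be completed online, and the recruitment text offers the 6-month questionnaire online or by telephone. The SAP is written in the past tense; if data collection is complete, only the SAP changes can be applied, and scores not collected cannot be recovered.

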**FORM: Application for Human Research**

NUMBER	FORM DATE	PAGE
F200		16 of 18

- v) Trained sonographers will perform the ITU utilizing the GENII system.
- vi) Disposal issues are not relevant to the use of the GEN II system.

SECTION 4: LIST OF ATTACHMENTS FOR THIS SUBMISSION

Document Name	Version Date
1. F107 v030614	1. 3/6/14
2. [name] CV_Nov 2013	2. 11/2013
3. Ortho - Planters Fasciitis Broch_v7	3. 2/2014
4. Craig's List	4. 3/4/14
5. T502a - ICF Consent Form v031014	5. 3/10/14
6. T504a - PHI Authorization Form v031014	6. 3/10/14
7. T504b- PHI Autorizacion Spanish v031414	7. 3/14/14
8. map	8. 9/23/13
9. ITU protocol [name] final	9. 4/5/14
10. AE Log	10. 4/5/14
11. NSR Statement 022614	11. 2/26/14
12. ITU-PF patient Instructions	12. 3/10/14

Submission List for F200: Application for Human Research**Required items for all F200 submissions:**

- F107: Verification of Training Form
- Current PI/Co-PI CVs or biosketch, if not included with copy of grant application

**FORM: Application for Human Research**

NUMBER	FORM DATE	PAGE
F200		17 of 18

Other Items as applicable:

- **Biosafety Review letter** (for UA - Institutional Biosafety Committee)
- **Certificate of Confidentiality**
- **Compressed Gases Review letter** (for UA – Research Instrumentation)
- **Contract** – complete or draft copy of contract including budget
- **Data Collection Tools** – surveys, questionnaires, diaries not included in the protocol, data abstraction form for records review
- **Data Monitoring Charter and Plan**
- **Drug/Device information** – Investigator's Brochure, drug product sheet, device manual, user's manual, instructions for use, package insert, IND/IDE documentation, FDA 1572 form, 510k indication, FDA exemption, sponsor determination of device risk, etc.
- **Export Control Review**
- **Grant Application(s)** – complete copy of grant, regardless of home institution or funding agency, and a copy of the Notice of Grant Award
- **Informed Consent/Permission/Assent Form(s)** – including study specific release of information documents, DHHS approved sample consent forms. If consent will not be documented in writing, a script of information to be provided orally to subjects
- Other Approval letters (e.g., school districts, Tribal, other IRB approvals)
- **Participant Materials** – All written materials to be provided to or meant to be seen or heard by subjects (e.g. study newsletter, physician to participant letter, wallet cards, incentive items, holiday/birthday cards, certificates, instructional videos/written guides, calendars, certification of achievement, etc.)
- **PHI Authorization Form(s)**
- **Protocol** – including all amendments/revisions, sub- or extension-studies
- **Radiation Safety Review letter**
- **Recruitment Materials** – telephone scripts, flyers, brochures, websites, email texts, radio/television spots, newspaper advertisements, press releases, etc.
- **Scientific Review Committee** letter (for cancer related projects – AZCC SRC; other units as applicable if the unit has a scientific review committee)
- **Site Authorizations** for research purposes and/or access to administrative records/samples
 - External sites (such as schools, other hospitals or campuses, etc.)
 - UAHN University Campus, South Campus and clinics Site Review Authority (SRA) approval
- **Supplemental site information** (for sites engaged in research where the UA is the IRB of record)
 - Copy of any approvals granted from that site (including determinations if this site has an IRB of its own)
 - Site-specific F107
 - Copy of the site's human subjects training policy
 - CV and medical license (if applicable) of site PI
- **Travel Authorization documentation** (for UA – Office of Global Initiatives)
- **Use of retrospective research samples and/or data** – IRB approval letter, original consent under which samples/data were collected, letter allowing access to samples

